3.5.5 Per Protocol Set (PPS)

Due to early termination of the study, the analyses planned using the PPS will no longer be performed.

3.5.6 Pharmacokinetic Set (PKS)

The PKS will consist of all subjects from the SS who provided at least 1 valid post-dose plasma concentration of unconjugated rotigotine.

Due to early stopping of the study, the analyses planned using the PKS will no longer be performed.

3.6 Treatment assignment and treatment groups

The treatment comparisons of primary interest will be each rotigotine group versus placebo. All summaries/analyses will generally be performed using the randomized treatment, i.e., placebo, rotigotine 2mg/24h and rotigotine 3mg/24h independent from the dose of administration.

3.7 Center pooling strategy

Not applicable.

3.8 Coding dictionaries

Adverse events and medical history will be coded using the most recent version of Medical Dictionary for Regulatory Activities (MedDRA 25.1). Prior or concomitant medication will be coded using the most recent version of the World Health Organization Drug Dictionary (WHO DD MAR/2022).

3.9 Changes to protocol-defined analyses

Statistical analysis and generation of tables, figures, subject data listings, and statistical outputs will be performed using SAS Version 9.3 or higher. None of the planned analyses require SAS Version 9.4 and can all be performed on SAS Version 9.3.

Analyses will not be performed as defined in the study protocol due to early study termination. All data will be listed and key summary tables will be produced.

4 STATISTICAL/ANALYTICAL ISSUES

4.1 Adjustments for covariates

Not applicable.

4.2 Handling of dropouts or missing data

Subjects who prematurely discontinue the study will be evaluated based on the data collected at each visit attended. If the premature discontinuation occurs at a scheduled visit, data collected at that visit will be summarized at the scheduled visit time point. Otherwise, the data will be attributed to the next scheduled visit for the purpose of by-visit endpoint summaries.

With respect to AEs, events with missing intensity will be assumed to be severe. Events with missing relationship to study medication per the investigator will be assumed to be related. Events with a missing answer to the question "Serious Adverse Event?" will be considered serious.

4.2.1 Missing efficacy data

For subjects who prematurely withdraw for any reason before EoM, values for planned efficacy assessments scheduled at subsequent visits will not be imputed. Efficacy assessments must be performed no later than 1 day after the last patch removal to be utilized for analysis (valid measurements).

For IRLS analysis, if any item is missing, the IRLS sum score will not be calculated. Missing IRLS baseline items and therefore the total score will be regarded as an important protocol deviation.

4.2.2 Missing and Incomplete Dates for Adverse Events and Concomitant Medication

For analyses of AEs and concomitant medication usage, a complete date must be established in order to correctly identify the AE or medication as occurring during treatment in the study or not. For the purposes of imputing missing date or missing components of partially-reported start and stop dates for AEs and for medication use, the algorithms listed below will be followed. Start and stop dates of AEs or concomitant medication will be displayed as reported in the subject data listings (i.e., no imputed values will be displayed in data listings).

- Missing start day, but month and year present:
If the first patch application occurred in the same month and year as the occurrence of the AE/medication, the start day of the event/medication will be assigned to the day of first patch application.
Otherwise the start day will be set to the 1st day of the month.
- Missing start day and month, but year present:
If the first patch application occurred in the same year as the occurrence of the AE/medication, the start day and month will be assigned to the date of first patch application.
Otherwise the start day and month will be set to January 1st.
- Missing end day, but month and year present:
The end day will be set to the last day of the month.
- Missing end day and month, but year present:
The end day and month will be set to the date of study termination or the date equivalent to 30 days after last patch removal, whatever occurs later.
However, if the study termination year and year for the date which is 30 days after the last patch removal are greater than the event/concomitant medication year, the day and month are to be set to December 31st.
- Completely missing start date:
An AE will be considered as occurring during treatment.
Medications with an unknown stop date or a stop date after the date of the first patch application will be considered as concomitant medication but not as prior medication. Medications with a stop date prior to first patch application will be considered as prior medication but not as concomitant medication. For these cases, impute the day and month to January 1st of the year of the first patch application.
- Completely missing stop date:
Adverse events with a completely missing stop date will be considered ongoing.
- Imputed stop date prior to imputed start date:

If the year of start date is the same as the year of first patch application and the stop date is after the date of first patch application, then set the start date to the date of first patch application.

Otherwise, set the start day and month to January 1st of the start year.

In the event of ambiguity or incomplete data which makes it impossible to determine whether a medication was concomitant, or an adverse event was treatment emergent, the medication will be considered as concomitant or the adverse event will be considered treatment emergent.

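### The year-only end-date rule in SAP 4.2.2 fails when study termination and last patch removal + 30 days straddle a year end, and can remove a partially dated adverse event from the TEAE counts

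*SAP*

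**What the plan says.** SAP 4.2.2 completes partial dates so that each adverse event (AE) and medication can be placed on or off treatment. Five of its rules matter here.

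- **Year-only end, default.** The end day and month are "set to the date of study termination or the date equivalent to 30 days after last patch removal, whatever occurs later". The wording covers day and month only, so read literally the recorded year stays.
- **Year-only end, exception.** December 31 is used "if the study termination year and year for the date which is 30 days after the last patch removal are greater than" the recorded year. Both years must exceed it.
- **Partial start.** With month and year known, the start takes the first-patch day if the month and year match first patch. "Otherwise the start day will be set to the 1st day of the month". With only the year known, the rule reads "If the first patch application occurred in the same year as the occurrence of the AE/medication, the start day and month will be assigned", the assigned value being first patch; in any other year the start is January 1.
- **Imputed stop before imputed start.** The first branch opens "If the year of start date is the same as the year of first patch application and the stop date is after the date", meaning first patch, and moves the start to first patch. The second branch reads "Otherwise, set the start day and month to January 1st of the start year".
- **Ambiguity clause.** It opens "In the event of ambiguity or incomplete data which makes it impossible to determine whether a medication was concomitant" and covers TEAE status in the same way; such a record counts as concomitant or treatment-emergent.

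SAP 10.2 then judges TEAE status mainly on onset: from first patch up to 30 days past last removal, or worsening of an earlier unresolved event. SAP 6.4 calls a medication concomitant if it was used at any time in the Treatment Period.

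**The concern.** The default and the exception test different dates. Requiring both years to exceed the recorded year amounts to testing the earlier of the two dates, while the default takes its day and month from the later one. When the dates lie either side of New Year, the two rules do not meet: the exception is off, and the default borrows a day and month from a year that is not the recorded one.

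Occurrence of TEAEs is a primary safety variable (Protocol 4.2.1), and the TEAE tables survive the cut-down after early termination (SAP 10.2). Elsewhere the SAP resolves missing AE information conservatively: under SAP 4.2, missing intensity becomes severe, missing relationship becomes related and missing seriousness becomes serious. This branch works the other way. Listings show dates as reported, so the imputed date that drove a classification would not be visible.

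**Working it through.** The rule carries no stated figure to reproduce, so the check is to run it on dates. The dates below are illustrative. Study termination is taken as the subject's own termination date.

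**Notation.** Y = recorded end year; R = last patch removal; P = R + 30 days; T = study termination; L = the later of T and P.

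**Rule as written.** If year(T) > Y and year(P) > Y, the end is 31 December Y. Otherwise the end is the day and month of L, in year Y. It goes wrong when the earlier of T and P is in Y and L is in Y + 1.

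**Worked cases** (recorded end 2021 in all four):

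| | T before P, straddle | P before T, straddle | Control: both in 2022 | Control: both in 2021 |
|---|---|---|---|---|
| First patch | 1 Sep 2021 | 10 Aug 2021 | 1 Sep 2021 | 1 Jun 2021 |
| R | 20 Dec 2021 | 28 Nov 2021 | 20 Dec 2021 | 19 Sep 2021 |
| P | 19 Jan 2022 | 28 Dec 2021 | 19 Jan 2022 | 19 Oct 2021 |
| T | 21 Dec 2021 | 2 Jan 2022 | 20 Jan 2022 | 20 Sep 2021 |
| Recorded start | Oct 2021 | Oct 2021 | Oct 2021 | Jul 2021 |
| Exception fires | no | no | yes | no |
| Imputed end | 19 Jan 2021 | 2 Jan 2021 | 31 Dec 2021 | 19 Oct 2021 |
| Imputed start | 1 Oct 2021 | 1 Oct 2021 | 1 Oct 2021 | 1 Jul 2021 |
| Stop before start | yes | yes | no | no |
| Final start | 1 Jan 2021 | 1 Jan 2021 | 1 Oct 2021 | 1 Jul 2021 |
| TEAE | **no** | **no** | yes | yes |

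Columns 1 and 3 hold the same event and the same exposure. Only the termination date differs, and the event's status flips.

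**Can the straddle occur?** Yes. Roll-over to RL0007 may take place at any time before the Safety Follow-Up Visit (Protocol 8.5), and subjects may withdraw, so T can precede P. The follow-up visit is 30 ± 5 days after the end of taper, so T can also follow P.

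**Exposed window.** Let T = R + t days.

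- For t up to 30, R must lie between 2 December and 31 December minus t days, which is 30 − t days.
- For t above 30, the window is t − 30 days.
- t = 0 gives 30 days (30/365 = 8.2%); t = 6 gives 24; t = 25 gives 5; t = 30 gives 0; t = 35 gives 5.

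A sweep assumed completers with R 110 days after first patch, first patch on each day of one year, and t from 0 to 35. That is 36 × 365 = 13,140 combinations. Straddles number (30 + 29 + … + 1) + 0 + (1 + … + 5) = 465 + 15 = 480, or 3.7%. With Y equal to the earlier year and a partial start, the literal rule lost the TEAE in all 480. These are combinations of dates, not a forecast of subjects.

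**Medications.** Here the stop date matters directly. With column 1 dates, a medication started in 2020 and recorded as ending in 2021 gets a stop of 19 Jan 2021, before first patch on 1 Sep 2021. It is then classed as prior only.

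**Completely missing AE start.** SAP 4.2.2 counts the event as on treatment, but SAP 10.2 tests the end date, so a January end would count against it there. The two sections disagree in this case.

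**The case against.** The strongest reply is that the rule was meant to assign the full later date. In column 1 the end would then be 19 Jan 2022, the stop-before-start rule would not be triggered, and the event would stay a TEAE. That reading is possible, but the text speaks of day and month, and it would give an event recorded as ending in 2021 an end in 2022. The sentence needs repair on either reading.

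Second, the ambiguity clause favours treatment-emergent status, and the SAP does not say whether it applies before or after the algorithm. It may well cover a record with both dates known only by year. It does not clearly cover a recorded on-treatment month, because status is then determinable and the algorithm overrides it.

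Third, the conditions are narrow. AEs are assessed at nearly every visit, so year-only end dates should be uncommon. All AEs are listed, so a misclassified event remains visible even though its imputed date does not. The remaining analysis is descriptive and no hypothesis test is affected. All of this stands, and it limits the size of the problem.

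A reader might infer that 8.2% of subjects are exposed, or that every AE in a straddle is lost. The documents support neither. The 8.2% is the share of calendar days when termination falls on the removal day, and it shrinks with every day termination moves towards day 30. An AE with a complete start date keeps its TEAE status, although its imputed end would precede its start.

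**Conclusion.** The point holds as a defect in a stated rule, at low priority. An AE with a recorded on-treatment start month is lost from the TEAE counts only if all of these apply:

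- the end date is known by year only;
- T and P fall in different years;
- the recorded end year is the earlier of the two;
- the start date is partial;
- day and month are read literally.

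If the full later date is assigned instead, TEAE status is kept but the recorded year is contradicted. The documents give no count of such records, and the number is likely to be small. Nothing here bears on the efficacy summaries.

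**What to change.** Replace the exception in SAP 4.2.2 with: if the later of the study termination date and the date 30 days after last patch removal falls in a year after the recorded end year, set the day and month to December 31 of the recorded year; otherwise keep the recorded year with the day and month of the later date.

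In columns 1 and 2 this gives an end of 31 Dec 2021 and leaves the start at 1 Oct 2021, so both events stay TEAEs. Both controls are unchanged, because the new wording alters only straddling records.

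Two tempting alternatives should be avoided.

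- **Taking the earlier of December 31 and the later date.** This overwrites the recorded year when an event ends after both dates, which Protocol 11.1.3 allows for. With P = 1 Dec 2021, T = 5 Dec 2021 and recorded end 2022, it gives 5 Dec 2021; the wording above gives 5 Dec 2022.
- **Restricting the January 1 start reset to recorded stop dates.** With first patch 1 Sep 2021, start 2021 and end March 2021, the present rules impute 1 Sep and 31 Mar, then reset the start to 1 Jan, which is correctly pre-treatment. Blocking the reset would make that event a TEAE. Leave this rule as it is.

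The cost is one sentence in the SAP and one condition in the date-imputation code. SAP 1 requires amendments to be final before database lock.

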11.1 Adverse events

11.1.1 Definitions

11.1.1.1 Adverse event

An AE is any untoward medical occurrence in a patient or clinical investigation subject administered a pharmaceutical product that does not necessarily have a causal relationship with this treatment. An AE can therefore be any unfavorable and unintended sign (including an abnormal laboratory finding), symptom, or disease temporally associated with the use of a medicinal (investigational) product, whether or not related to the medicinal (investigational) product.

In order to ensure complete safety data collection, all AEs occurring during the study (ie, after the signing of the Informed Consent form), including any pretreatment and posttreatment periods required by the protocol, must be reported in the eCRF even if no IMP was taken but specific study procedures were conducted. This includes all AEs not present prior to the initial visit and all AEs that recurred or worsened after the initial visit.

Signs or symptoms of the condition/disease for which the IMP is being studied should be recorded as AEs only if their nature changes considerably or their frequency or intensity increases in a clinically significant manner as compared to the clinical profile known to the investigator from the subject's history or the Baseline Period.

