10.2 Adverse events

Adverse events will be documented throughout the entire study on an ongoing basis. TEAEs are defined as events that started during the Treatment Period or within 30 days following the end of the Treatment Period (i.e., on or after the date of first patch application and within 30 days following the date of last patch removal) or any unresolved event already present before administration of treatment that worsens in intensity following exposure to the treatment. For AEs with a partial or missing start date, the imputation rules as described in [Section 4.2.2](#) will be applied.

Adverse events with a missing start date are defined as treatment-emergent if the end date of the AE is not on or before the date of first patch application.

An AE with action taken regarding study medication reported on the AE page of the eCRF as “drug permanently withdrawn” will be regarded as an AE leading to discontinuation of study medication.

Adverse events which have the question “Serious Adverse Event?” answered “yes” or missing are considered serious.

Treatment emergent AEs will be tabulated by MedDRA SOC, High Level Term (HLT) and PT. The number and percentage of subjects experiencing each event at least once will be summarized in addition to the number of events. In summaries of TEAEs by relationship and intensity, respectively, the number of events will not be presented.

All summaries will be sorted alphabetically by SOC and HLT and by frequency of events (PT) in the total rotigotine group within HLTs. If there is more than one PT with the same frequency in the total rotigotine group these events will be sorted alphabetically.

An overview of the incidence and frequency of all TEAEs, serious TEAEs, TEAEs leading to discontinuation of study medication, related TEAEs, severe TEAEs, all deaths and TEAEs leading to death will also be provided.

The following tabular summaries will be presented also.

- TEAEs
- TEAEs by intensity
- TEAEs by maximum intensity
- TEAEs by relationship to study medication per the Investigator
- Serious TEAEs
- Serious TEAEs by Relationship to study medication per the Investigator
- non-serious TEAEs above reporting frequency threshold of 5%

Individual subject data listings will be presented for all AEs.

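### SAP 4.2.2 and 10.2 give different answers for an adverse event with no start date that ended on or before the first patch, and neither section says which one governs

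*SAP*

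**What the plan says.** Two current sections of the SAP deal with an AE that has no start date.

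Section 4.2.2, in its item on completely missing start dates, gives one unconditional rule for AEs: "An AE will be considered as occurring during treatment". The end date plays no part. The medication rule in the same item does use it: "Medications with a stop date prior to first patch application will be considered as prior medication but not as concomitant medication".

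Section 10.2, which defines treatment-emergent AEs (TEAEs), says that AEs lacking a start date "are defined as treatment-emergent if the end date of the AE is not on or before the date of first patch application". The paragraph before that sentence also points back to the other section: "For AEs with a partial or missing start date, the imputation rules as described in" 4.2.2 are to be used. No order of precedence is given in either place.

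The general definition in 10.2 takes events that start from first patch application up to 30 days after last patch removal, together with unresolved earlier events that worsen after exposure.

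**The concern.** The two rules cover the same events and can return different flags. Two programmers could each follow the SAP and disagree. The unconditional rule in 4.2.2 also gives an answer that cannot be right for an event known to have ended before the first patch: it did not start on treatment, and it was no longer there to worsen.

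Events of this kind can be in the data. Protocol 11.1.1.1 has AEs recorded from consent, "including any pretreatment and posttreatment periods required by the protocol, must be reported in the eCRF". AEs are assessed at Visits 1 and 2, before the first patch at Visit 3. The 28-day screening maximum runs to Visit 2 rather than to first patch, and consent may precede the screening assessments, so no fixed length is put on this window here.

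The occurrence of TEAEs is a primary safety variable (protocol 4.2.1). Early termination has reduced the SAP to listings and key summary tables (SAP 3.9), and the TEAE tables by arm remain among its main comparative outputs.

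**Working it through.** There is no power or error-rate figure to reproduce. The check sets the two rules side by side for an AE with no start date, over every possible end date.

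1. **Ended before the day of first patch.** 4.2.2: on treatment. 10.2: not a TEAE. The rules conflict, and 4.2.2 also contradicts the general TEAE definition.
2. **Ended on the day of first patch.** 4.2.2: on treatment. 10.2: not a TEAE. The rules conflict. Here the event could have begun after application on that same day, so its true status is open.
3. **Ended after the day of first patch.** Both rules: TEAE. They agree.
4. **No end date, or ongoing.** 4.2.2 treats an AE with no end date as ongoing. Both rules: TEAE. They agree.
5. **Partial end date.** It is first completed under 4.2.2 (for example, a missing day becomes the last day of the month) and then falls under case 1, 2 or 3.

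The rules therefore disagree exactly when the known or imputed end date is on or before the day of first patch.

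**Is 4.2.2 really about TEAE status?** It speaks of occurring during treatment, not of being treatment-emergent. But its stated purpose is to complete dates "in order to correctly identify the AE or medication as occurring during treatment in the study or not", and its closing paragraph applies to the treatment-emergent decision by name. It is the same decision.

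**Does the closing default of 4.2.2 settle it?** That default begins "In the event of ambiguity or incomplete data which makes it impossible to determine whether a medication was concomitant" and extends to whether an AE was treatment-emergent. It applies only when status cannot be determined. In case 1 the end date determines it, so the default is not triggered and does not justify a TEAE flag. In case 2 the default would point to TEAE while 10.2 says otherwise, so the same-day boundary needs one stated answer.

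**A further loose end.** The same item ends with an instruction to impute a start of January 1st in the year of first patch. It reads as belonging to medications. If it were applied to AEs, it would usually put the start before first patch, against the rule that opens the item.

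**Size.** One reclassified subject changes an arm's TEAE incidence by at most 1/n, and only if that subject has no other TEAE in the same table row.

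- Planned size: 138 randomized / 3 arms = 46 per arm; 1/46 = 0.0217, about 2 percentage points.
- Assumed 20 per arm after early termination: 1/20 = 5 percentage points.
- Assumed 10 per arm: 1/10 = 10 percentage points.

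The equal split over three arms follows from the plan of 45 evaluable per group. The SAP states no achieved number, so 20 and 10 only illustrate a range.

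**The case against.** The strongest reply is that the correct exclusion is already in the SAP, in the section that defines TEAEs and governs their tables. Section 10.2 points to 4.2.2 for general imputation and then adds a specific rule for missing start dates. Reading the specific rule as qualifying the general one is natural. The log for SAP Amendment 2 lists the missing-start-date instructions in 4.2.2 and the TEAE clarification in 10.2 in the same revision, which fits their being read together. The closing default of 4.2.2, limited to undeterminable cases, points the same way. This reply stands as the likely intent. It does not remove the conflict, because neither section says that 10.2 prevails and 10.2 itself invokes 4.2.2.

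The second reply is that the practical effect is very small. The event needs an early end date, no start date (not even a year), and survival through the data checks in protocol 12.3.2. The TEAE tables are descriptive, and every AE is listed with its dates as reported. This stands in full.

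Two stronger readings should be resisted. A reader might infer that the SAP will count pre-treatment events as treatment-emergent. The documents do not support that, since it happens only if the 10.2 condition is ignored. A reader might also take a shift of 10 percentage points as the expected effect. It needs an arm of 10 subjects, a number that appears nowhere in the documents.

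**Conclusion.** The inconsistency is real but minor. It is a stated rule that conflicts with another stated rule, not a missing detail. For AEs with no start date that ended on or before first patch, 4.2.2 and 10.2 disagree; for those that ended before that day, 4.2.2 taken alone gives the wrong answer under the SAP's own definition. The end-date check in the adjoining medication rule suggests that its absence for AEs is an oversight.

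The direction of any error is known: following 4.2.2 can only add TEAEs. Its amount is not known, because the documents give no count of such events, but it is likely to be little or nothing. The per-subject bound of about 2 points rests on the planned allocation, and the 5 to 10 points on assumed arm sizes. No test or study decision depends on it.

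**What to change.** Make the AE rule in SAP 4.2.2 conditional: an AE with no start date counts as on-treatment unless its end date, reported or imputed, is on or before the day of first patch. That matches 10.2 as it stands. Alternatively, have 4.2.2 refer AEs with no start date to 10.2 and say that 10.2 governs. In the same edit, state that the January 1st imputation is for medications only, if that is what is meant.

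This repair leaves the boundary where 10.2 puts it. The sponsor may prefer to count events that ended on the day of first patch, since they could have started after application. That would move events from non-TEAE to TEAE and is a separate change of definition, to be declared as such and worded identically in both sections.

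The cost is one sentence in a SAP amendment, which SAP section 1 allows before database lock, and a matching check in the TEAE program. No new data are needed.
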